8.5.1 Early Termination Visit

Subjects may discontinue from the study or discontinue the study treatment only and continue to participate in the study.

Subjects who prematurely discontinue from the study should undergo final study assessments according to the following guidelines:

- Subjects discontinued from the study during the initial treatment period on/before the Week 16 visit should attend an ET visit. A follow-up/final visit is required 12 weeks after the last study drug administration.
- Subjects discontinued from the study during the maintenance period should attend an ET visit.

A follow-up/final visit is required 12 weeks after the last study drug administration.

Subjects who prematurely discontinue the study drug will be asked to continue participation in the study and return for all remaining visits and assessments (including daily assessment of pruritus, sleep disturbance, etc). Participation will continue until the subject completes the final study visit or otherwise discontinues study participation.

Subjects requiring rescue medication (with or without study medication discontinuation) may be eligible for LTE study participation:

- Subjects requiring rescue medication during the initial treatment period should continue with study visits including the Visit 6/Week 16. A follow-up/final visit is not required for subjects participating in the LTE study.
- During the maintenance period, for subjects requiring rescue medication before the Week 32 visit, a wait period with continuing study visits until the Week 32 visit is due is required. Thereafter, no wait period is required. Subjects must complete the final study/ET assessments prior to rollover to the LTE study.

A follow-up visit is not required for subjects who will participate in the LTE.

CONFIDENTIAL

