	Intercurrent events: use of rescue therapies prior to Week 16 is considered as non-responder; the observed response at Week 16 after treatment discontinuation will be used in the analysis.
	Summary measure: treatment difference of nemolizumab and placebo in response rate
Proportion of subjects with PP NRS < 2 at Week 16	Population: ITT population (Full population; Baseline PP NRS ≥ 7)
	Endpoint: a binary response indicates if subjects with PP NRS < 2 at Week 16
	Intercurrent events: use of rescue therapies prior to Week 16 is considered as non-responder; the observed response at Week 16 after treatment discontinuation will be used in the analysis.
	Summary measure: treatment difference of nemolizumab and placebo in response rate
	Population: ITT population (Full population; Baseline PP NRS ≥ 7)

This document is confidential.

1.0

CD14152.SPR118161.SAP.V01

Approved 10-Nov-2022 00:00:00

Endpoints	Estimands
Proportion of subjects with an improvement of SD NRS ≥ 4 at Week 16	Endpoint: a binary response indicates if subjects with an improvement of SD NRS ≥ 4 at Week 16
	Intercurrent events: use of rescue therapies prior to Week 16 is considered as non-responder; the observed response at Week 16 after treatment discontinuation will be used in the analysis.
	Summary measure: treatment difference of nemolizumab and placebo in response rate
Proportion of subjects with an improvement of PP NRS ≥ 4 at Week 4	Population: ITT population (Full population; Baseline PP NRS ≥ 7)
	Endpoint: a binary response indicates if subjects with an improvement of PP NRS ≥ 4 at Week 4
	Intercurrent events: use of rescue therapies prior to Week 4 is considered as non-responder; the observed response at Week 4 after treatment discontinuation will be used in the analysis.
Proportion of subjects with PP NRS < 2 at Week 4	Population: ITT population (Full population; Baseline PP NRS ≥ 7)
	Endpoint: a binary response indicates if subjects with PP NRS < 2 at Week 4
	Intercurrent events: use of rescue therapies prior to Week 4 is considered as non-responder; the observed response at Week 4 after treatment discontinuation will be used in the analysis.
Proportion of subjects with an improvement of PP NRS ≥ 4 at Week 2	Population: ITT population (Full population; Baseline PP NRS ≥ 7)
	Endpoint: a binary response indicates if subjects with an improvement of PP NRS ≥ 4 at Week 2

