8.2. Key Definitions

Screening Period is a Period of approximately 2-4 weeks before Day 1/Baseline during which subject eligibility is evaluated and standardized background topical therapy is introduced over a run-in Period of at least 2 weeks before Day 1/Baseline.

The Initial Period is defined as Day 1/Baseline to Week 16 (before the Week 16 dose, with last dose at Week 12). If early discontinued during treatment period, it is defined as the period until 4 weeks after last dosing date or early termination date whichever is earlier.

The Maintenance Period is defined as Week 16 (Maintenance Baseline) to Week 48. If early discontinued during treatment period, it is defined as the period until 4 weeks after last dosing date or early termination date whichever is earlier.

Follow-up Period is defined as the post end of treatment period (i.e., 1 day after end of treatment period) to Follow-up visit in respective treatment period.

The Baseline value of the Initial Period will be taken as latest valid value prior to first injection of study drug. For subjects randomized but not treated, the Baseline value will be the latest value prior to the randomization. Week 16 measurements will serve as Baseline measurements for the Maintenance Period (i.e., Maintenance Baseline). If Week 16 measurements are missing for re-randomized subjects, the last valid non-missing measurement in the Initial Period (i.e., before the dosing for Maintenance Period at Week 16 visit) will be taken as the Baseline measurement for the Maintenance Period.

For diary data (e.g., Peak Pruritus (PP) NRS, Sleep disturbance (SD) NRS), the Baseline values will be the weekly prorated average of non-missing subject diary scores reported during the 7 days. A minimum of 4 daily scores out of the 7 days is required to calculate the weekly prorated average score. Refer the details for the analysis visit window for diary data in Section 8.4.

The date of first treatment is defined as the date of first injection of study drug. The date of first treatment is the Baseline date.

The date of last treatment is defined as the date of last injection of study drug.

Study day is defined as the number of days from the date of first treatment and will be calculated as follows:

This document is confidential.

- If the event date \geq date of first treatment, study day = event date – date of first treatment + 1. Study Day 1 is therefore defined as the day of first treatment.

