For the evening assessments (PP NRS, AP NRS) during Initial Period, the daily data collected up to Week 16 will be classified into analysis visits considering the data during the 7 days immediately preceding the target study day of analysis visit. Similarly, for the morning assessment (SD NRS, morning sleep diary) during Initial Period, the 7 days data up to the target study day will be classified into analysis visit. Details of the analysis visit window are in the table below. Only the data belongs to Initial Period will be considered for classifying the analysis visit in Initial Period.

Table 8-2: Analysis Visit Window for Evening and Morning Assessments during Initial Period

Analysis Visit	Target Study Day of Analysis Visit	Visit Window for evening assessment (PP NRS, AP NRS, Topical Medication)	Visit Window for morning assessment (SD NRS, morning sleep diary)
Baseline*	1	-7 to -1	-6 to 1
Week 1	8	1 to 7	2 to 8
Week 2	15	8 to 14	9 to 15
Week 3	22	15 to 21	16 to 22
Week 4	29	22 to 28	23 to 29
Week 5	36	29 to 35	30 to 36
Week 6	43	36 to 42	37 to 43
Week 7	50	43 to 49	44 to 50
Week 8	57	50 to 56	51 to 57
Week 9	64	57 to 63	58 to 64
Week 10	71	64 to 70	65 to 71
Week 11	78	71 to 77	72 to 78
Week 12	85	78 to 84	79 to 85
Week 13	92	85 to 91	86 to 92
Week 14	99	92 to 98	93 to 99
Week 15	106	99 to 105	100 to 106
Week 16**	113	106 to 112 before dosing	107 to 113

* if there are less than 4 days non-missing data available within window, the lower bound of interval will be extended up to 7 additional days to obtain 4 days non-missing data for Baseline weekly score calculation. The timeframe window will not be considered.

** if <4 days non-missing data within Week 16 window, the upper bound will be extended first up to +5 days to obtain 4 non-missing data. If still <4 non-missing data after extending the upper bound, the lower bound will be extended again up to +5 days to obtain 4 days non-missing data. For evening assessment, only the data before Week 16 dosing (or re-randomization if missing Week 16 dosing) will be considered for Initial Treatment Period analysis.

This document is confidential.

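### Read literally, the SAP's Initial Period cut-off removes Week 16 itch and sleep diary scores from subjects who stop drug by Week 8 but stay in the study, against its own treatment-policy estimand

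*SAP*

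**What the plan says.** Four rules meet here.

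- **Estimand (SAP section 7).** Table 7-1 handles treatment discontinuation by treatment policy. Tables 7-2 and 7-3 repeat this for the co-primary and Week 16 key secondary endpoints, including those based on PP NRS and SD NRS: "the observed response at Week 16 after treatment discontinuation will be used in the analysis".
- **Data collection (Protocol 8.5.1).** "Subjects who prematurely discontinue the study drug will be asked to continue participation in the study and return for all remaining visits and assessments". The same sentence names the daily pruritus and sleep assessments, so the off-drug diary is meant to exist.
- **Period definition (SAP 8.2).** The Initial Period normally runs from Day 1 to Week 16, before the Week 16 dose. For a subject who is *early discontinued* during the treatment period, "it is defined as the period until 4 weeks after last dosing date or early termination date whichever is earlier". The text does not say whether stopping drug or leaving the study triggers this.
- **Diary windows (SAP 8.4, Table 8-2).** "Only the data belongs to Initial Period will be considered for classifying the analysis visit in Initial Period". The Week 16 evening window (PP and AP NRS) is "106 to 112 before dosing"; the morning window (SD NRS) is Days 107 to 113. If fewer than four days are available, the upper bound is extended first, and then "the lower bound will be extended again up to +5 days to obtain 4 days non-missing data". SAP 8.2 also states: "A minimum of 4 daily scores out of the 7 days is required to calculate the weekly prorated average score".

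Under SAP 8.3, a missing binary outcome in the Initial Period is a non-response. Table 8-1 windows IGA and EASI by study day (Week 16 is Days 99 to 126) and carries no such period restriction.

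**The concern.** The last two rules can remove exactly the data that the first two call for. A subject who stops drug after the Week 8 dose and fills in every diary entry to Week 16 would have no Week 16 itch or sleep score and would be scored a failure. The same subject's Week 16 EASI and IGA would be used. Someone off drug could therefore count as an EASI-75 responder for the co-primary and still be forced to fail the EASI-75 plus PP NRS composite.

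Three of the affected endpoints stand first in the key secondary order, which SAP section 10 tests sequentially and stops at the first failure. The sensitivity analyses share the input: LOCF, multiple imputation and the tipping-point analysis would all treat a recorded score as missing.

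**Working it through.** **Inputs.** Doses on Day 1 and at Weeks 4, 8 and 12 are nominal Days 1, 29, 57 and 85 (SAP Tables 4-1 and 8-1). Visit windows are ±3 days at Weeks 4 and 8 and ±5 days at Week 12 (Protocol 8.1.2). The period, window and minimum-day rules are those given above.

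**Step 1: reproduce Table 8-2.** Target day = 7 × week + 1, so Week 16 is 7 × 16 + 1 = 113. Evening window: 113 − 7 = 106 to 113 − 1 = 112. Morning window: 113 − 6 = 107 to 113. Both match the table. With the five-day lower extension they start at 106 − 5 = 101 and 107 − 5 = 102. The upper extension reaches only later days, so it cannot help a period that closes early.

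**Step 2: period end = last dose day + 28.** The last four columns count Week 16 diary days that fall inside the period; at least 4 are needed.

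| Last dose | Day | Period closes | Evening 106-112 | Evening from 101 | Morning 107-113 | Morning from 102 |
|---|---|---|---|---|---|---|
| Baseline | 1 | 29 | 0 | 0 | 0 | 0 |
| Week 4 | 29 | 57 | 0 | 0 | 0 | 0 |
| Week 8 | 57 | 85 | 0 | 0 | 0 | 0 |
| Week 8, 3 days late | 60 | 88 | 0 | 0 | 0 | 0 |
| Week 12, 5 days early | 80 | 108 | 3 | 8 | 2 | 7 |
| Week 12 | 85 | 113 | 7 | not needed | 7 | not needed |

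The early termination limb can only shorten the period further.

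**Step 3: threshold.** Four evening days from Day 101 need a period end of at least Day 104, so a last dose on Day 76 or later (104 − 28). Four morning days from Day 102 need Day 105, so Day 77 or later. A Week 8 dose would have to be 76 − 57 = 19 days late to reach this. Protocol 8.4.7 does allow dosing outside the visit window, so the zero-day result assumes doses given within it.

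**Step 4: endpoints.** Of the nine key secondary endpoints in SAP 10.2, five use the Week 16 diary: PP NRS improvement ≥4, PP NRS <2, SD NRS improvement ≥4, EASI-75 with PP NRS improvement, and IGA success with PP NRS improvement. The other four are at Weeks 1, 2 and 4. A subject dosed only on Day 1 is covered to Day 29, which includes the Week 4 windows (Days 22-28 and 23-29), so these four are untouched.

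**Step 5: effect on the treatment difference under non-responder imputation.** Let f be the share of an arm that is off drug by Week 8, still reporting and free of rescue, and r the response rate in that share. The change in the difference (nemolizumab minus placebo) is −(f_N × r_N − f_P × r_P). All values of f and r are assumptions.

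- f equal in both arms, r = 20% in both: change 0.
- r_N = 50%, r_P = 20%: −0.3 points at f = 1%, −0.9 at 3%, −3.0 at 10%.
- Unequal shares, f_N = 1%, f_P = 3%, r = 20% in both: −(0.2 − 0.6) = +0.4 points.

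**The case against.** The strongest reply is that the text need not be read this way. *Early discontinued* is undefined, and Protocol 8.5.1 separates stopping drug from leaving the study. If only study withdrawal is meant, a subject who stops drug and completes Week 16 is not cut. The restriction in SAP 8.4 may also have been meant only to divide diary entries before and after Week 16 dosing; the footnote to Table 8-2 and the text on topical medication point that way. The four-week cut reappears only for procedures and medications (SAP 9.4 and 9.5).

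This is a fair account of likely intent, but it is not what the text says. The four-week limb takes effect only for someone still in the study more than 28 days after the last dose, which most naturally describes a subject off drug but in follow-up. It could also describe someone who stops, stays and withdraws later, so it does not settle the matter. The pre-dosing rule is already stated separately, and no visible text exempts off-drug subjects. The SD NRS section (10.3.4) is redacted and could not be checked.

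The limits on the consequences stand. Rescue users are failures anyway. The tipping-point display covers every combination of responders among missing subjects, so it spans the lost outcomes, and the imputation model may add the number of injections.

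A reader might infer more, without support:

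- *That the rule biases the result towards nemolizumab through MMRM.* In SAP 10.3.3, MMRM is used for continuous change in PP NRS; it is not an analysis of these binary endpoints.
- *That the main and sensitivity analyses target different estimands.* The same scores drop out before LOCF, multiple imputation, tipping-point and non-responder analyses, which then differ only in how they treat the gap.
- *That phase 2b implies about 20 of 750 affected subjects.* The subtraction 226 − 176 − 44 = 6 (2.7%) sets treatment completion against study discontinuation and assumes everyone who left the study also failed to complete treatment. That study ran to Week 24, and Protocol 6.2.3 gives no timing of stops.

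**Conclusion.** The point holds as a conflict between stated rules. Applied literally, and with doses inside the visit windows, SAP 8.2 and 8.4 leave no usable Week 16 PP NRS or SD NRS day for a subject whose last dose was at Week 8 or earlier, even if the diary is complete. That contradicts Tables 7-1 and 7-3 and differs from how Table 8-1 treats IGA and EASI. It cannot be said with certainty that all such subjects will lose their scores, because the trigger is undefined.

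Five of nine key secondary endpoints are exposed; the co-primaries and the Week 1, 2 and 4 endpoints are not. Non-response is forced in both arms, so the effect on the difference is probably neutral or conservative. It could go the other way only if placebo lost the larger share of responders. If the drug had no effect, both arms would lose outcomes alike, so this is not type I error inflation.

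The number affected cannot be derived from the documents. As an assumption, 1-3% of the 500 nemolizumab subjects (750 × 2/3) would be 5-15, fewer once rescue users are set aside. The point merits correction, but it does not threaten the primary result.

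**What to change.** In SAP 8.2 and 8.4:

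- State that the cut at last dose plus four weeks serves only to assign medications, procedures and safety events to periods.
- State that for efficacy, including the diary data in Table 8-2, the Initial Period runs from Day 1 to the Week 16 visit (before Week 16 dosing or re-randomization) or study exit, whether or not study drug was stopped.
- Say whether *early discontinued* refers to drug or study.

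An off-drug subject who keeps reporting then has all seven days of each Week 16 window, as the estimand requires. The cost is a sentence or two in the SAP and a changed period flag in the diary dataset. No new data are needed, because the protocol already asks for these entries.

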8.5. Pooling of Centers

Centers will not be pooled.

8.6. Subgroups

Descriptive summary and analysis for primary and selected key secondary endpoints will be produced for the following subgroups:

- Region (Europe, North America, Asia Pacific)
- Age groups (12-17, 18-65, and > 65)
- Sex
- Race
- Baseline IGA (3 or 4)
- Baseline PP NRS (≥ 7 and < 7)
- Previous use of any systemic therapy for AD (Yes, No)
- Previous use of any biologic therapy for AD (Yes, No)
- Previous use of any immunosuppressive or immunomodulatory drugs for AD (Yes, No)
- Previous use of Dupilumab for AD (Yes, No)
- Previous use of Cyclosporine for AD (Yes, No)
- Country

This document is confidential.

9. Demographic, Other Baseline Characteristics and Medication

Subject accounting, disposition, demographics, Baseline characteristics, previous therapies, and concomitant therapies by treatment will be summarized for the Initial Period and Maintenance Period.

9.1. Subject Disposition and Withdrawals

All subjects who provide informed consent will be accounted for in this study.

Subject accounting will summarize subjects screened, screen failed, randomized and randomized but not treated for the Initial Period for all subjects by overall and site. For the Maintenance Period subject randomized and subjects randomized but not treated will be summarized by overall and site, and all placebo-treated subjects will also be included for the summary.

Subject accounting by visit will be summarized by treatment group and overall for the Initial Period and the Maintenance Period at each visit (scheduled visits only).

Subject disposition will be summarized based on the ITT population by treatment group for the Initial Period and the Maintenance Period. Summaries will include subjects randomized, subjects randomized but not treated, subjects treated, subjects completed treatment, subjects discontinued treatment, primary reason for discontinuation of treatment (including summary of subjects who stopped treatment due to COVID-19), subjects completed the study, subjects discontinued from the study, primary reason for discontinuation from the study (including summary of subjects who discontinued due to COVID-19), subjects rolled over to long term extension (LTE), subjects completed Follow-up. Subjects who stopped treatment or discontinued study due to COVID-19 will be identified using "Other" specify field in CRF or "Comment as needed".

Subject disposition will also be summarized by site on the ITT population.

Screen failure will be summarized for all screened subjects. Number of subjects screened and failed will be presented. Number and percentage of reason for screen failure will be summarized.

Subjects in each analysis population (ITT, Safety, PK, and PP population only for Initial Period) will be summarized by treatment group on the ITT population for each period.

In addition, time (days since the first dose of study drug) to permanent discontinuation of study drug by reason for discontinuation will be displayed graphically in subjects having permanently discontinued from the study drug.

Maintenance Period summary will include all subjects either who completed the Initial Period and re-randomized to the Maintenance Period or who received Placebo in both Initial and Maintenance Period.

Randomization, study completion, drug completion, visit dates will be listed for the ITT population. Screen failure reason will also be listed. Additional listings of discontinuation reason, missed visit and missed assessment for subjects who discontinued due to COVID-19 will be presented for the ITT population. An additional listing for Covid-19 relevant comments will be presented for the ITT population.

Analysis population will be summarized and listed on the ITT population.

This document is confidential.

9.2. Demographic and Baseline Characteristics

All variables will be summarized by treatment group at Baseline and Maintenance Baseline respectively. Summary statistics for demographic and other Baseline characteristics will be presented for the ITT, SAF, PP and PK population.

Age (years), height (cm), weight (kg), and BMI (kg/m²) will be summarized using summary statistics for continuous variables. Age groups (12-17, 18-65, and > 65), sex, region (Europe, North America, Asia Pacific), country, race, ethnicity, and smoking status will be summarized using the summary statistics for categorical variables. Weight and BMI will additionally be presented for each age group. For the summary of height, weight and BMI in Maintenance Period, Maintenance Baseline will be used.

The Baseline disease characteristics, EASI, IGA, weekly average PP-NRS, PP-NRS (<7 and ≥7), weekly average AP-NRS, weekly SD-NRS, BSA (%) involvement of AD, SCORAD, pain frequency and intensity, DLQI and cDLQI will be summarized. IGA will be summarized as a categorical variable. For Maintenance Period, Maintenance Baseline will be used to summarize.

A summary table for the stratification factors will be provided to show any discrepancies between what was reported through Interactive Voice Response System (IVRS)/Interactive Web Response System (IWRS) versus stratification using actual data at Baseline. Actual PP-NRS score will be derived using the diary data.

All demographic and baseline characteristics data will be listed on the ITT population.

9.3. Medical History

Medical history will be collected only at screening and will be coded using Medical Dictionary for Regulatory Activities (MedDRA, Version 25.0, March 2022).

Medical history will be summarized by treatment group and period. The summary will include number and percentage of subjects reporting each system organ class (SOC) and preferred term (PT) and will be sorted alphabetically by SOC and descending frequency of PT within SOC in the Nemolizumab 30mg Q4W group. Summary tables will be presented for the ITT population.

Medical history data listings will be presented by subject number, period, start date, stop date, SOC, and PT for the ITT population.

